11.1.3 Recording Adverse Events

Event reporting will extend from time of informed consent until completion of the final visit. Serious adverse events occurring after the end of the clinical trial must be reported if the Investigator considers there to be a causal relationship with the Investigational Product.

SAE Notification Form should be used to report any related SAEs which occur after the end of the clinical trial.

Adverse events (AEs) should be recorded on the AE eCRF, whether believed by the Investigator to be related or not related to the Investigational Product.

AE reporting should contain;

- a brief description of the event,
- date of onset,
- date of resolution,
- severity,
- actions taken or treatment required,
- relationship to Investigational Product,
- outcome, and
- whether the event is considered serious.

Whenever possible, the Investigator should group signs or symptoms that constitute a single diagnosis into a single event term. For example, "cough, rhinitis, and sneezing" might be grouped together as "upper respiratory tract infection".

Asymptomatic abnormal findings considered by the Investigator to be clinically significant should be recorded as an AE, unless it is associated with a clinical syndrome that has already been reported as an AE.

11.1.4 Reporting Serious Adverse Events

All SAEs that occur during the period of observation, whether considered to be related to the Investigational Product or not, must be reported within 24 hours of awareness or knowledge of the event. The date the site personnel became aware of the serious adverse event must be recorded in the source document. To report the SAE, complete the eCRF AE page and indicate the reason for seriousness. The minimum information required for an initial report is:

- Sender of report (name, address of Investigator)
- Subject identification (screening/randomization number, initials, NOT subject name)
- Protocol number
- Description of SAE (e.g., event term)
- Seriousness criteria
- Relationship assessment

After receipt of the initial report, the Medical Monitor or designee will review the information and, if necessary, contact the Investigator to obtain further information for assessment of the event. The Sponsor or designee will be responsible for information processing and reporting in accordance with applicable local and regulatory requirements.

The Sponsor or designee will determine if an SAE requires expedited reporting to regulatory agencies. The clinical trial site personnel are responsible for reporting these events to their EC/IRB according to the institution's EC/IRB reporting requirements and in accordance with applicable local and regulatory requirements.

Should the EDC System not be available, serious adverse events must be reported on the paper SAE Notification Form. Additional details can be found in the Site Manual. This does not replace the EDC reporting system; information must be entered in the EDC system once the system returns to normal function.

11.1.5 Unexpected and Related Serious Adverse Events

Unexpected SAEs are those which:

- Are not previously reported as associated with ALD403, as referenced in the Investigator's Brochure.
- May be symptomatically and pathophysiologically related to an AE listed in the Investigator's Brochure, but differ from the event due to greater severity, frequency or specificity.

The Sponsor or designee will report, to the appropriate regulatory authorities according to local and regulatory requirements, unexpected SAEs which are considered related to ALD403 (suspected unexpected serious adverse reactions [SUSARs]). The clinical trial site personnel are responsible for reporting these events to their EC/IRB in accordance with applicable local and regulatory requirements.

11.1.6 Follow-up of Adverse Events

Irrespective of the suspected causality, AEs will be monitored until resolution, stabilization in the judgment of the Investigator, or the subject is lost to follow up or withdraws from the trial.

11.1.7 Clinical Laboratory Tests

Serum chemistry tests include albumin, alkaline phosphatase (ALP), alanine aminotransferase (ALT), aspartate aminotransferase (AST), urea nitrogen, calcium, bicarbonate, creatinine, globulin, glucose, phosphorus, potassium, sodium, total bilirubin, total cholesterol, total protein, triglycerides, magnesium and uric acid.

Hematology tests include hematocrit, hemoglobin, mean corpuscular hemoglobin (MCH), mean corpuscular hemoglobin concentration (MCHC), mean corpuscular volume (MCV), platelet count, red blood cell (RBC) count, RBC morphology, and white blood cell (WBC) count with differentials (neutrophils, lymphocytes, monocytes, eosinophils, and basophils).

11.1.8 Pregnancy

In the event that a female subject becomes pregnant following administration of Investigational Product(s) or may have been pregnant at the time of Investigational Product(s) exposure, or the partner of a male subject becomes pregnant following administration of Investigational

Product(s), the pregnancy must be reported to the Sponsor within five business days of the Investigator becoming aware of the pregnancy. Pregnancy information will be reported to the Sponsor using the Exposure In-Utero Forms.

Although pregnancy *per se* is not considered an AE, the outcome of a pregnancy that results in a birth defect or congenital anomaly or hospitalization for any reason is considered to be an SAE. Every attempt should be made to follow a pregnancy to conclusion.

Follow-up information is to be collected by the Investigator and provided to the Sponsor regarding;

- the course of the pregnancy including; perinatal and neonatal outcome, or premature termination of the pregnancy, or miscarriage
- offspring information including; birth weight, and birth defects (if any)

11.1.9 Suicidal Ideation and Behavior

Recent meta-analyses, spontaneous reports, and published case reports regarding suicidal ideation and behavior arising from drugs tested in clinical trials have been noted as an area of general concern. Based on this information, the United States Food and Drug Administration (FDA) has provided guidance to prospectively assess suicidal ideation and behavior in clinical trials to ensure that subjects in clinical trials who are experiencing suicidal ideation and behavior are properly recognized and adequately treated and to ensure the collection of more timely and more complete data on suicidal ideation and behavior than have been collected in the past ¹³. The C-SSRS (Columbia-Suicide Severity Rating Scale) will be used for this purpose. Any subject who answers 'yes' to questions 4 or 5 of the C-SSRS during the screening visit will be referred to a mental health specialist by the investigator. During the course of the trial after dosing, any subject who answers 'yes' to questions 4 or 5 of the C-SSRS will be discontinued from the study treatment and referred by investigators to a mental health specialist.

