- 12. The subject is at imminent risk of self-harm or harm to others in the investigator's opinion, based on clinical interview and responses provided on the Columbia-Suicide Severity Rating Scale (C-SSRS). Subjects must be excluded if they report suicidal ideation of Type 4 or 5 (i.e., suicidal ideation with intent, with or without a plan) in the past 6 months or suicidal behavior in the past 2 years, as measured by the C-SSRS at Screening or Baseline.
- 13. Any history or evidence of substance abuse (e.g., alcohol, opiates, and barbiturates) within the past 2 years according to the International Classification of Diseases (ICD) 10: F10-19.¹²

- 14. Pregnant, breastfeeding, or planning to become pregnant during the trial
- 15. Receipt of any experimental, unregistered therapy (within or outside a clinical trial) within 30 days or 5 plasma half-lives (whichever is longer) before screening
- 16. Receipt of any monoclonal antibody treatment within 6 months of screening (within or outside a clinical trial)
- 17. Previously dosed with ALD403 or any monoclonal antibody targeting the CGRP pathway
- 18. Planned or current participation in any other clinical trial during the duration of this clinical trial, or within 6 months of screening
- 19. Recent or planned surgery, requiring general anesthesia, within 8 weeks prior to screening and during the duration of this clinical trial
- 20. Positive for HIV, hepatitis B surface antigen, or hepatitis C antibody at screening
- 21. Employees of the sponsor, CRO, or any clinical trial site involved in this trial and their immediate family members (i.e., parents, spouse, siblings, children)

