15.2.2 Since Last Visit Version

COLUMBIA-SUICIDE SEVERITY

RATING SCALE

(C-SSRS)

Since Last Visit

Version 1/14/09

Posner, K.; Brent, D.; Lucas, C.; Gould, M.; Stanley, B.; Brown, G.; Fisher, P.; Zelazny, J.; Burke, A.; Oquendo, M.; Mann, J.

Disclaimer:

This scale is intended to be used by individuals who have received training in its administration. The questions contained in the Columbia-Suicide Severity Rating Scale are suggested probes. Ultimately, the determination of the presence of suicidal ideation or behavior depends on the judgment of the individual administering the scale.

Definitions of behavioral suicidal events in this scale are based on those used in The Columbia Suicide History Form, developed by [name] and [name], Conte Center for the Neuroscience of Mental Disorders (CCNMD), New York State Psychiatric Institute, [name]. (Oquendo M. A., Halberstam B. & Mann J. J., Risk factors for suicidal behavior: utility and limitations of research instruments. In M.B. First [Ed.] Standardized Evaluation in Clinical Practice, pp. 103-130, 2003.)

For reprints of the C-SSRS contact [name]., New York State Psychiatric Institute, [name]; inquiries and training requirements contact [contact]

© 2008 The Research Foundation for Mental Hygiene, Inc.

SUICIDAL IDEATION		
Ask questions 1 and 2. If both are negative, proceed to "Suicidal Behavior" section. If the answer to question 2 is "yes", ask questions 3, 4 and 5. If the answer to question 1 and/or 2 is "yes", complete "Intensity of Ideation" section below.	Sin La Vis	st
1. Wish to be Dead		
Subject endorses thoughts about a wish to be dead or not alive anymore, or wish to fall asleep and not wake up.	Yes	No
Have you wished you were dead or wished you could go to sleep and not wake up?		
If yes, describe:		
2. Non-Specific Active Suicidal Thoughts		
General, non-specific thoughts of wanting to end one's life/commit suicide (e.g., "I've thought about killing myself") without thoughts of ways to kill oneself/associated methods, intent, or plan during the assessment period.	Yes	No
Have you actually had any thoughts of killing yourself?		
If yes, describe:		
3. Active Suicidal Ideation with Any Methods (Not Plan) without Intent to Act		

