Subject endorses thoughts of suicide and has thought of at least one method during the assessment period. This is different than a specific plan with time, place or method details worked out (e.g., thought of method to kill self but not a specific plan). Includes person who would say, "I thought about taking an overdose but I never made a specific plan as to when, where or how I would actually do itand I would never go through with it."	Yes	No
Have you been thinking about how you might do this?		
If yes, describe:		
4. Active Suicidal Ideation with Some Intent to Act, without Specific Plan		
Active suicidal thoughts of killing oneself and subject reports having some intent to act on such thoughts, as opposed to "I have the thoughts but I definitely will not do anything about them."	Yes	No
Have you had these thoughts and had some intention of acting on them?		
If yes, describe:		
5. Active Suicidal Ideation with Specific Plan and Intent		
Thoughts of killing oneself with details of plan fully or partially worked out and subject has some intent to carry it out.	Yes	No
Have you started to work out or worked out the details of how to kill yourself? Do you intend to carry out this plan?		

If yes, describe:			
INTENSITY OF IDEATION	,		
The following features should be rated with respect to the most severe type of and 5 being the most severe).	f ideation (i.e., 1-5 from above, with 1 being the least severe		
Most Severe Ideation:		Most Severe	
Description of Ideation	Type # (1-5)		
Frequency			
How many times have you had these thoughts?			
(1) Less than once a week (2) Once a week (3) 2-5 times in week	(4) Daily or almost daily (5) Many times each day		
Duration			
When you have the thoughts, how long do they last?			
(1) Fleeting - few seconds or minutes (4)	4-8 hours/most of day		
(2) Less than 1 hour/some of the time (5)	More than 8 hours/persistent or continuous		
(3) 1-4 hours/a lot of time			
Controllability			
Could/can you stop thinking about killing yourself or wanting to die if you	want to?		
(1) Easily able to control thoughts (4)	Can control thoughts with a lot of difficulty		
(2) Can control thoughts with little difficulty (5)	Unable to control thoughts		
(3) Can control thoughts with some difficulty (0)	Does not attempt to control thoughts		
Deterrents			
Are there things - anyone or anything (e.g., family, religion, pain of death) of committing suicide?	- that stopped you from wanting to die or acting on thoughts		

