(1) Deterrents definitely stopped you from attempting suicide (4)) Deterrents most likely did not stop you		
(2) Deterrents probably stopped you (5)) Deterrents definitely did not stop you		
(3) Uncertain that deterrents stopped you (0)) Does not apply		
Reasons for Ideation			
What sort of reasons did you have for thinking about wanting to die or killi feeling (in other words you couldn't go on living with this pain or how you from others? Or both?			
(1) Completely to get attention, revenge or a reaction from others (4)	Mostly to end or stop the pain (you couldn't go on		
(2) Mostly to get attention, revenge or a reaction from others	living with the pain or how you were feeling)		
(3) Equally to get attention, revenge or a reaction from others (5)	(you couldn't go on		

and	d to end/stop the pain	living with the pain or how you were feeling)		
		(0) Does not apply		
SUICIL	DAL BEHAVIOR		Sin	ice
Actual At	tempt:			
kill oneselt suicide atte	f. Intent does not have to be 100%. If there	t some wish to die, as a result of act. Behavior was in part thought of as method to is any intent/desire to die associated with the act, then it can be considered an actual or harm, just the potential for injury or harm. If person pulls trigger while gun is in insidered an attempt.	Yes	No
example, a	highly lethal act that is clearly not an accid	ish to die, it may be inferred clinically from the behavior or circumstances. For lent so no other intent but suicide can be inferred (e.g., gunshot to head, jumping denies intent to die, but they thought that what they did could be lethal, intent may be		
Have you	made a suicide attempt?			
Have you o	done anything to harm			
Have you	done anything dangerous where you could	have died?		
Wh	at did you do?			
Did	you as a way to end your life?		Total	# of
Did	you want to die (even a little) when you_	?	Atte	npts
Wei	re you trying to end your life when you	?		
Or a	did you think it was possible you could hav	ve died from?		_
-		ithout ANY intention of killing yourself (like to relieve stress, feel o happen)? (Self-Injurious Behavior without suicidal intent)		
If yes, desc	cribe:		Yes	No
Has subj	ject engaged in Non-Suicidal Self-I	njurious Behavior?	103	110
·				
Interrup	ted Attempt:			
	person is interrupted (by an outside circums e occurred).	stance) from starting the potentially self-injurious act (if not for that, actual attempt	Yes	No

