interrupted pulling trig	attempt. Shooting: Person has gun pointed gger. Once they pull the trigger, even if the	n ingesting. Once they ingest any pills, this becomes an attempt rather than an toward self, gun is taken away by someone else, or is somehow prevented from gun fails to fire, it is an attempt. Jumping: Person is poised to jump, is grabbed and ound neck but has not yet started to hang - is stopped from doing so.		
Aborted	Attempt:			
	e behavior. Examples are similar to interrup	icide attempt, but stops themselves before they actually have engaged in any self- ted attempts, except that the individual stops him/herself, instead of being stopped by	Yes	No

Preparatory Acts or Behavior:		
Acts or preparation towards imminently making a suicide attempt. This can include anything beyond a verbalization or thought, such as assembling a specific method (e.g., buying pills, purchasing a gun) or preparing for one's death by suicide (e.g., giving things away,	Yes	No
writing a suicide note).		
Suicidal Behavior:	Yes	No
Suicide:	Yes	No
Answer for Actual Attempts Only	Most Le Attempt	
Actual Lethality/Medical Damage:		
0. No physical damage or very minor physical damage (e.g., surface scratches).	Enter	Code
1. Minor physical damage (e.g., lethargic speech; first-degree burns; mild bleeding; sprains).		
2. Moderate physical damage; medical attention needed (e.g., conscious but sleepy, somewhat responsive; second-degree burns; bleeding of major vessel).		
3. Moderately severe physical damage; medical hospitalization and likely intensive care required (e.g., comatose with reflexes intact; third-degree burns less than 20% of body; extensive blood loss but can recover; major fractures).		
4. Severe physical damage; medical hospitalization with intensive care required (e.g., comatose without reflexes; third-degree burns over 20% of body; extensive blood loss with unstable vital signs; major damage to a vital area).		
5. Death		
Potential Lethality: Only Answer if Actual Lethality=0		
Likely lethality of actual attempt if no medical damage (the following examples, while having no actual medical damage, had potential for very serious lethality: put gun in mouth and pulled the trigger but gun fails to fire so no medical damage; laying on train tracks with oncoming train but pulled away before run over).	Enter	Code

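### The post-dose C-SSRS rule for stopping treatment and referring covers two ideation questions but no suicidal-behavior item

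*Protocol*

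**What the plan says.** Protocol 11.1.9, which covers both suicidal ideation and behavior, explains that the scale is used so that subjects "experiencing suicidal ideation and behavior are properly recognized and adequately treated". Its only mandatory action after dosing is that those positive on "questions 4 or 5 of the C-SSRS will be discontinued from the study treatment and referred by investigators to a mental health specialist".

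The Since Last Visit form in Appendix 15.2.2 defines the items. Question 4 is headed "Active Suicidal Ideation with Some Intent to Act, without Specific Plan", and question 5 is ideation with a specific plan and intent. The behavior section comes later and rates actual, interrupted and aborted attempts and preparatory behavior, the last defined as "Acts or preparation towards imminently making a suicide attempt". The form's routing is "Ask questions 1 and 2. If both are negative, proceed to" the behavior section; the rater is told to "ask questions 3, 4 and 5" only when question 2 is positive. If a subject denies intent in an actual attempt, "it may be inferred clinically from the behavior or circumstances".

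At entry, exclusion criterion 12 (Protocol 8.2) removes subjects with Type 4 or 5 ideation "in the past 6 months or suicidal behavior in the past 2 years, as measured by the C-SSRS at Screening or Baseline".

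**The concern.** The section names behavior as part of its purpose, yet its action rule uses ideation items only. Read literally, it requires less for a rated suicide attempt than for ideation with some intent and no plan. Entry criterion 12 puts behavior beside Type 4/5 ideation, so the post-dose rule is also narrower than the entry rule. That is an asymmetry rather than a contradiction.

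Patient safety is at stake. The Week 12 and Week 36 visits (Protocol 10.5 and 10.10) list the C-SSRS among assessments done before that day's infusion. A subject rated positive for a preparatory act or attempt, but not for question 4 or 5, could be infused the same day and not referred, with no breach of 11.1.9.

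**Working it through.** The plan gives no figure to reproduce. The check is of the text, with one illustrative calculation.

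**1. Scope of the trigger**, counted from the Since Last Visit form:
- Ideation items in the trigger: 2 of 5 (questions 4 and 5).
- Behavior items in the trigger: 0 of 4 (actual attempt, interrupted attempt, aborted attempt, preparatory acts).

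**2. Can a behavior item be positive without question 4 or 5?** An attempt is defined by at least some wish to die, so many attempters should also be positive on question 4 or 5. The form leaves two ways around this.

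| Post-dose rating | Question 4 or 5 | Required by 11.1.9 |
|---|---|---|
| Type 4 ideation, no behavior | Yes | Stop and refer |
| Attempt, intent admitted | Probably yes | Stop and refer if yes |
| Attempt, intent denied but inferred by rater | May be no | Nothing |
| Any behavior item positive, question 2 negative | Not asked | Nothing |

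**3. Does another section supply the mandate?**
- Protocol 8.4.1 permits discontinuation for an adverse event or by investigator decision. The Medical Monitor discussion precedes removal from treatment; it does not trigger it.
- Protocol 8.4.2 does not list suicidal behavior as a reason for withdrawal from the trial.
- Protocol 11.2 calls for standard-of-care treatment of emergencies. It asks that discontinuation be considered for conditions the investigator believes are related to the product.
- Protocol 11.1.4 gives 24-hour reporting and Medical Monitor review for serious events. An aborted attempt or preparatory act without injury may be judged non-serious, because the important-medical-event criterion in 11.1.2 rests on medical judgment.
- Protocol 7.3 has the DMC review safety data periodically and advise on the trial. It is not a same-visit rule for one subject.
- SAP 3.6.6 only summarizes and lists C-SSRS results.

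None of these requires stopping or referral on a behavior item. That the matter is left to investigator judgment is an inference from 8.4.1 and 11.2; 11.1.9 does not say so.

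**4. Scale.** The documents give no event rate. Let *p* be the share of subjects ever rated positive on a behavior item after dosing, and *q* the share of those with no positive answer on question 4 or 5. Both are assumptions: *p* from 0.1% to 1%, *q* from 10% to 50%. With the planned 800 subjects, number affected = 800 × *p* × *q*:
- Low: 800 × 0.001 × 0.10 = 0.08
- High: 800 × 0.01 × 0.50 = 4

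**5. Reach of an amendment.** Footnote 2 to Table 5.3 says enrollment in this trial is complete, so an amendment reaches only subjects with visits still to come. The form is given at ten post-dose visits (Weeks 4, 8, 12, 16, 20, 24, 28, 36, 48 and 56), and the last infusion is at Week 36. At Weeks 48 and 56 no infusion remains to be stopped, and only the referral has effect.

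**The case against.** The strongest reply is that 11.1.9 aims at recognition and adequate treatment, not at automatic withdrawal of drug. Recognition is met, since the full form is given at every post-dose visit. An actual attempt would ordinarily be handled as an emergency under standard of care, and serious events reach the Medical Monitor within the reporting system. The form's disclaimer leaves ideation as well as behavior to the rater's judgment, so a rater who infers intent for an attempt could carry that into the ideation items. The skip route requires a subject to deny any thought of killing themselves and yet be rated positive for an attempt or preparatory act. The protocol reports no toxicity from CGRP blockade (5.4), and the range of 0.08 to 4 rests on assumed inputs.

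Much of this stands. The gap is narrow, a route to stop exists, the size cannot be established, and stopping helps only subjects with an infusion left. The reply does not remove the point, however. The sponsor chose a mandate over judgment for Type 4 and 5 ideation. The documents give no reason why an attempt or preparatory act should carry a weaker requirement, and none of the backstops requires a referral.

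**Conclusion.** The concern holds. The post-dose safety rule in 11.1.9 is too narrow for the section's stated purpose: it mandates stopping and referral for two ideation items and for none of the four behavior items, and the form allows a behavior rating that misses the trigger. This conclusion rests on the text alone and is firm.

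Its practical size is unknown and probably very small. The illustrative 0.08 to 4 subjects depends wholly on the assumed *p* and *q* and counts all 800 subjects; with enrollment complete, the number an amendment could still help is lower. No endpoint, efficacy analysis or error rate is affected. The change is worth making because it is cheap and the event concerned can be fatal.

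**What to change.** In the last sentence of Protocol 11.1.9, after the reference to questions 4 or 5, insert: *or who is rated positive on any suicidal-behavior item of the scale (actual, interrupted or aborted attempt, or preparatory acts; not non-suicidal self-injury)*. The existing consequence, stopping study treatment and referral, then applies to both groups.

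In 8.4.1, add one sentence outside the permissive list saying that treatment must be stopped for subjects who meet the 11.1.9 criteria. This is mainly a cross-reference, since 11.1.9 is already mandatory, but it stops 8.4.1 from being read as the whole rule.

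The cost is one amended and one added sentence in a protocol amendment. No new assessment is needed, because the behavior items are already collected and reported (SAP 3.6.6). The downside is possibly a few extra discontinuations or referrals. Data loss should be limited, because 8.4.1 encourages subjects who stop treatment to continue study assessments.
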